### 2.7 Subgroups for Analysis

The following subgroups will be performed for primary analysis to evaluate the safety and efficacy of MitraClip G4 system.

MitraClip usage:

*This confidential document is the property of Abbott and shall not be reproduced, distributed, disclosed or used without the express written consent of Abbott.*

## Statistical Analysis Plan

- G4NT
- G4XT
- G4NTW
- G4XTW

Etiology:

- DMR
- FMR
- Mixed

Anatomical Measurements such as Shorter Leaflet, Primary Jet A2-P2, Large Flail, Smaller MV Area (MVA < 4 cm^2), Mitral valve commissures will be analyzed by the following subgroups:

SLDA events:

- Subjects with SLDA
- Subjects without SLDA

Clip usage:

- G4NT
- G4XT
- G4NTW
- G4XTW

Use of the CGP feature and left atrium pressure monitoring will also be analyzed.

### 2.8 Handling of Missing Data

If Echocardiography assessed MR severity at discharge is unavailable or cannot be assessed, the 30-day value will be used to assess APS. All analyses will be based on available data with missing data excluded. Any unused or spurious data will be noted as appropriate.

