3.0 STUDY FLOW and FOLLOW-UP SCHEDULE

3.1 Number of Subjects to be Enrolled

In accordance with ISO 14155, subjects who have provided written informed consent are considered enrolled.

[figure not shown]
Upon echocardiographic verification that there is no evidence of intracardiac, inferior vena cava (IVC) or femoral venous thrombus per IFU requirements; the MitraClip procedure should be attempted for all enrolled patients. A procedure is considered attempted when the MitraClip delivery system is introduced into the femoral vein. Only enrolled patients with an attempted MitraClip procedure will be included in

Clinical Investigation Plan

the analysis population. Patients that have an attempted procedure, but no MitraClip implant will be followed for 30 days only for adverse events. Following the consent, if thrombus is identified at baseline and medically treated and resolved at a later date, a patient may be re-consented for the EXPAND G4 Study if they are eligible for a new attempted MitraClip procedure.

Up to █ consented subjects with confirmation of no thrombus who have a MitraClip procedure attempted will be included for analysis in the MitraClip G4 EXPAND Study. Phase II study will include █ subjects. The Study will be conducted at a maximum of █ centers in the EU, the US, Canada and Japan. A site maximum of █ subjects will be enforced so that no site will be permitted to submit data for more than █ of the study population.

Clinical Investigation Plan

FIGURE 2: Schematic for Study Inclusion and Flow

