3.2 Study Flow and Follow up Schedule

Consecutive eligible patients that present for MitraClip procedure should be consented for the MitraClip EXPAND G4 Study. Patients are included in the analysis upon completion of MitraClip G4 procedure.

Follow-up data on clinical assessment should be submitted at discharge, 30-day visit, 6-month phone call, 1 year, 2 year, 3 year, 4 year and 5 year visits. Echocardiograms are required to be submitted for the baseline, discharge, 30-day and 12-month and 5 year time points. All Echocardiograms conducted by the site during the study period (required by protocol or not) will be submitted to the Sponsor (see **Table 2**). Section 6.4 of this protocol provides more detail on follow-up visits.

The first █ subjects treated with the MitraClip G4 in the MitraClip EXPAND G4 Study in Europe with evaluable acute procedural success (APS) data will be included in the G4 PMCF Study as described in Appendix II. Subjects with evaluable echocardiograms may be selected for a more detailed assessment by an independent core lab.

A schematic of the study flow is shown in **Figure 2**.

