6.4 Subject Follow-up

Follow-up visits should be conducted per standard of care based on the follow up schedule outcomes in Table 2. During the follow-up period for this study (5 years) any unscheduled echocardiograms, either TEE or TTE, should be submitted.

All follow-up assessment, visit or phone, should include a review for adverse events occurring since the last visit. Results from the KCCQ survey are required to be recorded and submitted at the 30-day, 12-month and 2, 3, 4, 5-year visits. Visit should be scheduled relative to the date of the MitraClip Procedure. If a 6-minute walk test is conducted as standard of care and was conducted at baseline; results for 6-minute walk test at 30 day, 12-months and 2, 3, 4, 5-year visits will be collected in the EXPAND G4 Study.

Visits at:

- 30 days (-14 days / +60 days)
- 1, 2, 3, 4, 5 years (- 30 days / +90 days)

Phone call or visit at:

- 6 months (- 30 days / +90 days)

Clinical Investigation Plan

Table 2. Clinical Follow-Up Schedule

1. Adverse Events to be collected in this study include: all cardiovascular events, events classified as MAEs (as defined in section 4.1) and device-related adverse events (as defined in section 4.2).
2. TTE and TEE during treatment should be submitted for the study only if capturing TTE and TEE echoes is part of standard of care.

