8.2 Analysis Populations

All subjects who signed and dated an Inform Consent Form and were treated with a MitraClip G4 device will be included in the analysis.

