#### 1.4 Study Endpoints

The following study endpoints will be evaluated during the clinical trial for all Phase II subjects:

Safety: The assessment of safety will include all occurrences through 30 days post procedure.

- Occurrence of Major Adverse Events (MAE) at 30 days. MAE is defined as a composite of all-cause Death, Myocardial Infarction, Stroke, or non-elective Cardiovascular (CV) surgery for device related complications.

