## Statistical Analysis Plan

Performance: The assessment of performance measures will include all data reported at 30-day visits for this study.

- MR Reduction to ≤2+ at 30 days

Procedural endpoints:

- Acute Procedural Success (APS) defined as successful implantation of the MitraClip device with resulting MR severity of 2+ or less on discharge Echocardiogram (30-day echocardiogram will be used if discharge is unavailable or uninterpretable). Subjects who die or undergo mitral valve surgery before discharge are considered an APS failure.
- Acute Device Success defined as successful implant of the MitraClip device without the occurrence of a Device-Related Complication (including mitral valve stenosis, device embolization, Single Leaflet Device Attachment (SLDA), iatrogenic atrial septal defect, or myocardial perforation) through discharge.
- Procedure Time: defined as the time elapsed from the first intravascular catheter placement or trans-esophageal echocardiogram (TEE) to the removal of the last catheter and TEE
- Use of Controlled Gripper Actuation (CGA)
- Use of Left Atrial Pressure (LAP) Monitoring
- Number of Attempted Grasps defined as the number of attempts to stabilize leaflets by the open Clip
- In-hospital Major Adverse Events (MAE) defined as the number of MAEs that occur prior to discharge from hospitalization in which MitraClip Procedure was performed
  - *MAE is defined as a composite of all-cause Death, Myocardial Infarction, Stroke, or non-elective Cardiovascular (CV) surgery for device related complications.*

Clinical endpoints evaluated at discharge, 30 days, 1, 6 and 12 months, and 2, 3, 4, 5 years are:

- All-cause Mortality
- Heart Failure Hospitalization
- Occurrence of AE
- Device-Related Complications defined as the occurrence of one the following adverse events that is determined by investigator assessment to be probably, possibly or definitely related to the MitraClip device.
  - Mitral valve stenosis
  - SLDA
  - Device Embolization
  - Iatrogenic atrial septal defect
  - Myocardial perforation
  - Need for mitral valve replacement instead of repair due at least in part to the MitraClip procedure or the presence of the MitraClip device
- MR Reduction to ≤1+ (evaluated at discharge, 30 day, 1 year, 5 year)
- MR Reduction to ≤2+ (evaluated at discharge, 30 day, 1 year, 5 year)

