## 2.0 ANALYSIS CONSIDERATIONS

### 2.1 Analysis Populations

#### 2.1.1 Primary Analysis Population

A patient is considered enrolled upon signing and dating an informed consent form for participation. The primary analysis population will be defined as all enrolled subjects with a MitraClip G4 system implant procedure attempted.

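### The 30-day MR ≤2+ rate is planned for all attempted procedures but will in practice describe implanted survivors with an echocardiogram; an all-attempts rate should stand beside it

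*SAP*

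**What the plan says.** **Population.** SAP 1.4 introduces the endpoint list with "The following study endpoints will be evaluated during the clinical trial for all Phase II subjects". SAP 2.1.1 defines the primary analysis population as "all enrolled subjects with a MitraClip G4 system implant procedure attempted", and SAP 3.1 evaluates the listed Phase II endpoints in that population. Protocol 3.1 and 5.4 also use attempted procedures. Protocol 8.2 differs: it refers to subjects who "were treated with a MitraClip G4 device will be included in the analysis".

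**Measure.** For MR ≤2+ at 30 days, SAP 1.4 says: "The assessment of performance measures will include all data reported at 30-day visits for this study". It gives no rule for death, no implant or mitral surgery before that visit. The visit window in protocol 6.4 is "30 days (-14 days / +60 days"), that is, day 16 to day 90.

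**Follow-up.** Under protocol 3.1, patients with an attempt but "no MitraClip implant will be followed for 30 days only for adverse events". The one route to a 30-day MR grade for them is protocol 3.2: "All Echocardiograms conducted by the site during the study period (required by protocol or not) will be submitted to the Sponsor".

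**Missing data.** SAP 2.8 allows the 30-day echocardiogram to replace a missing discharge one for APS. For everything else the rule is "All analyses will be based on available data with missing data excluded". Protocol 8.4.3 and Appendix II 9.4.5 say the same.

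**APS, for contrast.** Its definition requires successful implantation and counts death or mitral surgery before discharge as failure.

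**PMCF population.** SAP 2.1.2 takes the first 420 subjects enrolled in Europe with an attempted procedure. Protocol 3.2 takes the first European subjects whose APS data are evaluable.

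**The concern.** The stated population and the available data do not match. A failed implantation and a death before the visit are both outcomes in which the performance goal of the procedure was not reached, yet each removes the subject from the rate instead of lowering it. The discrepancy can run in only one direction. Because protocol 1.0 plans to set outcomes against historical data, the denominator needs to be explicit.

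The same rule touches APS, the only endpoint with a hypothesis test. There the gap is narrower: it concerns only subjects who still have no readable echocardiogram after the 30-day fallback. If the PMCF set is chosen on evaluable APS data, as protocol 3.2 has it, these subjects never appear, and their possible effect on the test cannot be seen.

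**Working it through.** **1. Who leaves the 30-day rate.** An attempted subject contributes only with an MR grade from the 30-day visit. No-implant attempts have none planned, and subjects who die first have none. With missing data excluded, both go. The exception is a non-protocol echocardiogram in a no-implant subject.

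**2. Size of the difference.** Let R be the rate among subjects with an echocardiogram and d the share of attempts lost to no implant or death. Suppose live implanted subjects without an echocardiogram resemble those with one. Then the all-attempts rate is R × (1 − d), and the difference is R × d.

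For R, protocol 2.2 gives 90.1% (primary MR) and 96.3% (secondary MR) from the sponsor's study of the previous clip generation. Denominators are not stated, so I take these as rates among evaluable subjects.

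| d | R = 90.1% | R = 96.3% |
|---|---|---|
| 1% | 0.90 points | 0.96 points |
| 2% (assumed) | 1.8 points | 1.9 points |
| 3% (assumed) | 2.7 points | 2.9 points |

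**3. APS: the plan's own figure.** SAP 2.3–2.4 give a goal of 82.8%, an expected rate of 88%, a one-sided 5% exact test, 400 evaluable subjects and 90% power. The smallest passing count is 344/400 (size 0.049), with power 90.2%. The plan's figure is reproduced. Also 400 × 1.05 = 420.

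**4. APS: how many missing failures change the result.** A 5% loss from 420 leaves 399 evaluable and 21 missing. This is close to a ceiling, because SAP 2.4 states the 5% at discharge, before the 30-day fallback. All 420 subjects need at least 361 successes (p = 0.047); 360 gives p = 0.062.

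| Observed | Missing | Missing that fail | Result on 420 |
|---|---|---|---|
| 351/399 (88.0%, p = 0.003) | 21 | 11 | 361, p = 0.047, passes |
| 351/399 | 21 | 12 | 360, p = 0.062, does not pass |
| 361/410 (88.0%) | 10 | all 10 | 361, p = 0.047, passes |
| 371/399 (93.0%) | 21 | all 21 | 371, p = 0.001, passes |

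The third row is near the planning rate, with fewer missing. The last is near the 92.9% (962/1,035) reported for the previous generation. With 21 missing, every worst case passes once at least 361/399 (90.5%) succeed.

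**5. How likely a reversal is.** Take a true APS of 88% in evaluable subjects. If missing subjects fail at twice the 12% rate, the chance of passing on available data but not on all 420 is about 5% with 21 missing and 2% with 10. At three times the rate it is about 15% and 6%.

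**The case against.** The strongest reply is that the available-data rate is not wrong. The SAP says openly that it uses 30-day visit data, MR grade exists only in a living subject with an echocardiogram, and SAP 2.2 would show the number of observations. The rate is too high only when read as a rate for all attempts. This stands as far as it goes, and the available-data rate should stay. It does not remove the mismatch: SAP 1.4, 2.1.1 and 3.1 name all attempts as the population, and no 30-day MR rate is planned for it.

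Second, failed implants and in-hospital deaths count as APS failures, and deaths through day 30 count in MAE and all-cause mortality. SAP 2.3 tests no hypothesis for Phase II. This also stands, and it is why the point is an inexpensive improvement.

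Three stronger readings are tempting, and the documents do not support them:

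- *A large overstatement.* The early US registry in Appendix VI (implant rate 96.8%, 30-day mortality 5.8%) would give 1 − 0.968 × 0.942 = 8.8% leaving, and 0.963 × 8.8% = 8.5 points. That is earlier-device experience with independence assumed. Protocol 2.2 describes the previous generation's 30-day MAE rate as very low.
- *A fragile APS test.* Tipping at 12 of 21 means 57% failure among the missing against 12% among the observed. Missing-as-failure is an extreme bound, not a forecast.
- *A third PMCF population in SAP 1.3.* Its reference to 420 European subjects with the necessary data reads most naturally as the trigger for the analysis. The conflict is between protocol 3.2 and SAP 2.1.2.

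**Conclusion.** The main point holds. Followed as written, the plan gives a 30-day MR ≤2+ rate for essentially implanted survivors with an echocardiogram, while naming all attempted procedures as the population. As an all-attempts rate it errs upward by 0.90 to 0.96 points per 1% leaving. The share leaving in this study is unknown, and the 1.8 to 2.9 points at 2–3% is an illustration that rests on that assumption and on the previous generation's MR rates. A reader might infer that the study's performance conclusion is invalid; it is not, because the measure is descriptive and no decision rule depends on it.

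The APS point is secondary. The result could turn on missing subjects near the planning rate with about 21 missing, but not near the previous generation's rate. It covers only the readable text: parts of protocol Appendix II 9.2 to 9.4.1 and of SAP 2.3 are blank or redacted, and a sensitivity analysis may be there.

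**What to change.** 1. Keep the available-data 30-day rate for historical comparison, and label its denominator as implanted, alive and with an evaluable echocardiogram.
2. Beside it, report MR ≤2+ among all attempted subjects, counting no implant, death or mitral surgery before the 30-day echocardiogram (window to day 90) as not achieved. State how many live implanted subjects have no echocardiogram.
3. Reconcile the treated-subject population of protocol 8.2 with the attempted-procedure population used elsewhere.
4. Reconcile the PMCF population between protocol 3.2 and SAP 2.1.2. Use the SAP 2.1.2 set, with SAP 1.3 as the timing trigger, so that subjects missing APS stay visible.
5. Add a tipping-point table for APS, with missing-as-failure as its extreme bound. Leave the APS definition and the 82.8% goal unchanged.

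The cost is wording, two population reconciliations and two tables. Implant status, deaths and cardiovascular events are already collected; the case report forms are not shown, so capture of the date of mitral surgery should be confirmed. The downside is a somewhat lower all-attempts figure, which should not be the one compared with historical available-data rates.

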### 2.9 Multiplicity Issues

No multiplicity adjustment is needed for this EXPAND G4 Post Market Phase II study, because there is no pre-specified hypothesis test.

For the MitraClip G4 PMCF study, there is a single primary endpoint and hence no multiplicity adjustment is needed.

*This confidential document is the property of Abbott and shall not be reproduced, distributed, disclosed or used without the express written consent of Abbott.*

## Statistical Analysis Plan

### 2.10 Adjustments for Covariates

Unless otherwise specified, no adjustments for covariates will be made for any of the variables in the analyses.

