In more recent 2016 publication, Lesevic et al.¹⁴ retrospectively analyzed patients treated with the MitraClip® device and compared the procedural success, long-term outcomes, repair durability, and prognostic factors. Patients were grouped into the EVEREST group (N=59) or non-EVEREST group (N=75) according to the presence or absence of EVEREST inclusion criteria. Acute procedural success was achieved in 95.5% of patients with no difference between EVEREST (97%) and non-EVEREST (95%) patients. There was no statistically significant difference in the number of device implanted between the two groups. A similar mean acute MR reduction was achieved in both groups (-2.3 ± 0.9 vs -2.2 ± 1 , respectively; $p=0.497$). At a mean follow-up of 3.5 years, recurring MR $\geq 3+$ was more frequent in non-EVEREST patients than in EVEREST patients (28% vs 45%; $p=0.066$). Re-interventions for recurring MR were more frequently required in non-EVEREST patients than in EVEREST patients, including second MitraClip device interventions (2% vs 13%; $p=0.085$) and mitral valve surgeries (9% vs 28%; $p=0.047$). Flail width was found to be an independent predictor for re-intervention, whereas flail gap ≥ 10 mm displayed a strong trend (flail width: adjusted HR 11.2, 95% CI 2.6 to 48.3; $p=0.001$; flail gap: adjusted HR 3.1, 95% CI 0.9 to 11.5; $p=0.077$).

In addition, Abbott has initiated a large scale observational study (1000 patients) in US and EU (EXPAND) to evaluate the safety and performance of the MitraClip NTR/XTR system. The 30 day study outcomes were recently reported in ESC 2019¹⁵. The acute procedure success rate was 92.9% (962/1035) and 30 day major adverse event rate was very low. MR $\leq 2+$ at 30 day was achieved at 90.1% in primary MR patients and 96.3% in secondary MR patients. This study also characterized the baseline mitral valve anatomic features (assessed by the echo core-lab) associated with NTR and XTR clip selection. It was identified that MitraClip XTR (compared to NTR) was more often used in Primary MR in subjects with larger gaps. For secondary MR patients, XTR was used when there was significant leaflet tethering, particularly in the P2/P3 locations. Data presented in EuroPCR 2020¹⁶ showed that MR reduction with XTR clip size was more favorable in PMR subjects with more complex MV anatomies, larger prolapse, smaller ventricles and more severe MR. and thereby demonstrating the utility of XTR Clip in tailoring the therapy to individual's MV anatomy.

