2.3 Rationale for Conducting this Study

The primary objective of the MitraClip EXPAND G4 study is to confirm the safety and performance of the MitraClip® G4 System in a contemporary real-world setting. The rationale for conducting this study is as follows:

- This study will provide first-hand clinical evidence of safety and performance of these next generation MitraClip Systems.
- This study will satisfy post-market clinical follow-up (PMCF) required as a condition of CE Mark approval for the MitraClip G4 Systems. A subset of patients will be analyzed as part of the MitraClip G4 PMCF Study (Appendix II) to fulfill this requirement.
- The recent advancements with wider clip arms on MitraClip NTW and XTW, and the controlled gripper actuation (CGA) feature of the MitraClip G4 Systems may offer an advantage in leaflet approximation of certain mitral valve anatomies; this study will help to identify populations that can benefit most from these next generation MitraClip Systems.
- This study will generate prospective data to evaluate the clip selection and leaflet grasping technique recommendations generated by the MitraClip G4 Advisory board and provide validation through real-world outcomes.

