#### 2.2.1 Descriptive Statistics for Continuous Variables

For continuous variables (e.g., age, etc.), results will be summarized with the numbers of observations, means, and standard deviations, with quartiles, minimums, maximums, and 95% confidence intervals for the means. Differences between subgroups, where specified, will be summarized with relative risks, the differences of the two means, and 95% confidence intervals for the difference between the means.

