#### 2.2.2 Descriptive Statistics for Categorical Variables

For categorical variables (e.g. APS, etc.), results will be summarized with subject counts and percentages/rates, and where applicable, with exact 95% Clopper-Pearson confidence intervals, and p-values may be presented for hypothesis generating purposes. Differences between the two groups, when specified, will be summarized with the difference in percent and the Newcombe score 95% confidence interval for the difference of two percentages.

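### Clip-size summaries in the SAP are confounded by anatomy and have no rule for subjects with several clip sizes or no implant, so they cannot alone support the protocol's clip-selection aims

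*SAP*

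**What the plan says.** **Aims.** The primary objective is the safety and performance of the G4 system as a whole (Protocol 1.2, SAP 1.2). Protocol 1.0, 2.2 and 2.3 add further aims: to evaluate the advisory board's clip-selection recommendations against real-world outcomes and validate them, and to learn which anatomies suit the wider clips. In the words of Protocol 2.3, "this study will help to identify populations that can benefit most from these next generation MitraClip Systems".

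**Planned analyses.** SAP 2.7 says: "The following subgroups will be performed for primary analysis to evaluate the safety and efficacy of MitraClip G4 system". It lists clip usage (G4NT, G4XT, G4NTW, G4XTW) and etiology (DMR, FMR, mixed) as separate one-way groupings. It then tabulates anatomical measurements by SLDA status and by clip: "Mitral valve commissures will be analyzed by the following subgroups". No analysis crosses clip with etiology or anatomy for an outcome.

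**Adjustment.** SAP 2.10 states that "no adjustments for covariates will be made for any of the variables in the analyses". The sentence opens by allowing exceptions specified elsewhere, but the SAP specifies none.

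**Contrasts.** SAP 2.2.1 says "Differences between subgroups, where specified, will be summarized with relative risks, the differences of the two means", and SAP 2.2.2 says "Differences between the two groups, when specified, will be summarized with the difference in percent". Section 2.7 specifies no clip-versus-clip contrast. Phase II has no hypothesis test (SAP 2.3), although for categorical variables "p-values may be presented for hypothesis generating purposes".

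**Evidence on clip choice.** Protocol 2.2 reports from the predecessor study that "MitraClip XTR (compared to NTR) was more often used in Primary MR in subjects with larger gaps", and that in secondary MR the larger clip was used where tethering was significant.

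**The concern.** Operators pick the clip to fit the valve. If valve type also affects the result, a table of outcomes by clip size mixes the effect of the clip with the effect of the valve. The planned tables offer no way to separate them, because clip and etiology are each shown alone. Side-by-side clip columns will nevertheless be read as a comparison, and the protocol intends to use such results to judge the selection recommendations. A clip reserved for difficult valves could look worse, or one used in easy valves better, with no difference between the devices.

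The groups are also not fully defined. The analysis population is every attempted procedure (SAP 2.1.1). A subject with an NT and an XTW clip could be counted twice, once or not at all. A subject with no implant belongs to no clip group, yet fails APS by definition, because APS requires successful implantation (SAP 1.4).

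**Working it through.** **1. The plan's one powered figure.** This is the PMCF sample size: APS 88% against a goal of 82.8%, exact test, one-sided 5%. With n = 400 the smallest rejecting count is 344; the exact type I error is 0.0488 and the power 0.902. This reproduces the stated 90%, and 400 × 1.05 = 420. The test uses no clip subgroup, so nothing below affects it. The plan gives no sample size for the clip subgroups.

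**2. Spurious clip difference from etiology alone.**
Inputs: 30-day MR ≤2+ of 90.1% in primary and 96.3% in secondary MR (Protocol 2.2, predecessor study). The primary-MR shares a and b in two clip groups are assumptions; the documents do not give them. The true clip effect is set to zero.

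Rate in a group with primary share a = 0.901a + 0.963(1 − a), so the spurious difference = (0.963 − 0.901) × (a − b) = 0.062 × (a − b).

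| Primary-MR shares (assumed) | MR ≤2+ in each group | Spurious difference |
|---|---|---|
| 60% vs 40% | 92.6% vs 93.8% | 1.2 points |
| 70% vs 30% | 92.0% vs 94.4% | 2.5 points |
| 80% vs 20% | 91.3% vs 95.1% | 3.7 points |

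In the last row the apparent failure rate is 8.7% against 4.9%, a ratio of about 1.75, from case mix alone. If an unadjusted two-sided 5% test were run with 250 subjects per group (assumed), it would flag these differences about 8%, 20% and 38% of the time. Across 150 to 400 per group the range is 6% to 55%.

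**3. How firm the 6.2 points are.** They come from one study. Elsewhere the protocol reports no etiology difference in APS or post-procedure MR ≤2+ in the European pilot registry (Appendix II section 2.1, Appendix VI), and none that was significant in 30-day MR ≤2+ or APS in the Asia-Pacific registry (Appendix VI). With a gap of zero the formula gives zero. It also leaves out flail, tethering and other anatomy, which could add to the bias or offset it.

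**4. Subjects without a clear clip group.**
- Several sizes: subjects = 1,000 × (share with two or more clips) × (share of those with mixed sizes). The Asia-Pacific registry had 50.7% with two or more; the German registry reports only a mean of 1.4 ± 0.6 clips. Assuming 30% to 50.7% multi-clip use and 25% to 75% mixing gives 1,000 × 0.30 × 0.25 = 75 up to 1,000 × 0.507 × 0.75 = 380 subjects.
- No implant: implant rates in Appendix VI run from 96.8% to 99.6%. If these applied, 1,000 × 0.032 = 32 down to 1,000 × 0.004 = 4 subjects would have no clip.

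**The case against.** The other side has a good case on several points. Phase II is descriptive, no clip contrast is specified, and SAP 2.10 sets a default rather than a ban. The SAP tabulates anatomy by clip, so a reader can see imbalance. The larger clip in the predecessor study was chosen for anatomy in both etiologies, so a large difference in primary-MR share between clips is not established.

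All of this stands, and it rules out some stronger readings that a reader might infer:
- *The study compares clips with wrong intervals.* The difference interval in SAP 2.2.2 treats the two groups as independent, but it applies only when a contrast is specified, and none is for clips. The problem arises only if one is produced.
- *The clip groups overlap.* The SAP does not say so; assignment is undefined, and overlap is inferred from multi-clip use in earlier registries.
- *The study cannot answer its question.* Clip-by-anatomy benefit is not the primary objective, and baseline anatomy, clip use and outcomes are collected. The gap is in the planned analysis, not in the data.

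A full multivariable model for every endpoint would also go too far. SLDA rates of 0.7% to 4.2% in the protocol's registries mean about 7 to 42 events in 1,000 subjects. The anatomic criteria in Appendix VI tie coaptation measures to functional MR and flail measures to leaflet flail, so a pooled model would have covariates missing by design. Valve area is not a listed echocardiographic endpoint (SAP 1.4), though SAP 2.7 names it as an anatomical measurement.

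The descriptive label does not settle the matter. Seeing that anatomy differs between clips does not show how outcomes compare in similar valves, and one-way tables cannot deliver the validation that Protocol 2.3 promises.

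**Conclusion.** The point holds in a limited form. As planned, the clip-size summaries are confounded by indication for the protocol's aims on clip selection and anatomy, and the SAP contains no analysis that would serve those aims. Subjects with several clip sizes or no implant have no assigned group.

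The size is uncertain. It is 1.2 to 3.7 points on 30-day MR ≤2+ if the predecessor study's etiology gap holds and primary-MR shares differ by 20 to 60 percentage points between clips. It is near zero from this source if etiology does not matter. The shares and the mixing proportions are assumptions. The finding of confounding rests on the documented link between anatomy and clip choice, and on outcome varying with anatomy or etiology, which the protocol's sources report inconsistently. The primary objective and the PMCF test are not affected. The SAP should be amended before clip results are tabulated.

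**What to change.** **SAP 2.7.** Classify each subject once: NT only, XT only, NTW only, XTW only, mixed sizes, no implant. Show APS and 30-day MR ≤2+ and ≤1+ by clip class within the DMR, FMR and mixed strata. Keep the crude tables and label them non-comparative. Keep SLDA descriptive.

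**SAP 2.10.** Add one named exception: for these common endpoints, a supportive clip difference with its confidence interval, standardised or adjusted for etiology and baseline MR grade. Use flail or coaptation measures only within the etiology to which they apply. Restrict it to strata in which both clip classes occur, and state that it is exploratory.

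The table of recommendations in Appendix I is not visible in the public document, so whether agreement with them can be coded per subject cannot be judged here. If it can, outcomes by agreement would address the validation aim most directly.

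**Cost.** SAP wording, a few tables and one simple supportive model, using etiology, MR grade and clip data that are already in the plan. The price is wider intervals and sparse cells for the less used clips. Exclusive classes prevent double counting but do not remove all bias, since a second clip of another size may be added because the first result was poor.
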